2.2. PHASE 2A EXPANSION GROUPS

2.2.1. Objectives

2.2.1.1. Primary Objectives

- Further investigate the safety and tolerability profile of SQ3370 in anthracycline naïve patients with:
 - Group 1: Neo-adjuvant treatment of patients with STS of the extremity who are ineligible for primary surgical resection and under consideration for possible/probable amputation, with predefined anthracycline sensitive tumors.
 - Group 2: Patients with unresectable, locally advanced or metastatic STS, with predefined anthracycline sensitive tumors and compare safety and tolerability of the RP2D in two infusion schedules of SQP33 (3-day vs 5-day).
 - Group 3:
 - 3a) Patients with relapsed or metastatic squamous-cell head and neck cancer

2.2.1.2. Secondary Objective

- Assess preliminary signals of SQ3370 anti-tumor activity.
- Characterize the PK profile of SQP33 prodrug and active Dox following SQ3370 treatment.

2.2.1.3. Exploratory Objectives

- Assess the concentration of active Dox and SQP33 prodrug following SQ3370 treatment at the local site through analysis of tumor biopsies.
- Assess immune response through biomarker analysis of tumor biopsies and peripheral blood specimens.

2.2.2. Endpoints

2.2.2.1. Primary Endpoints

- Frequency of AEs and SAEs, as well as changes from baseline in vital signs, clinical laboratory parameters, physical examination findings, ECHO/MUGA, and ECG results across all treatment cycles and groups.

2.2.2.2. Secondary Endpoint

- ORR per RECIST v1.1.
- OS
- Time from enrollment to first subsequent therapy (TFST)
- Plasma concentration and PK parameters for SQP33 prodrug and active Dox following SQ3370 treatment.
- Group 1: Advanced High-risk Soft Tissue Sarcoma of the Extremity
 - Histopathological Response
 - Surgical outcome amputation/limb-salvage vs planned
 - Disease-free survival
 - Local recurrence-free survival [Time Frame: 2 years]
 - Distant recurrence-free survival
 - Symptomatic disease control
- Group 2: Comparison of the RP2D of SQ33 total dose in mg/m² administered every 21 days administered over 3 vs over 5 days
 - Compare safety and tolerability of two infusion schedules of SQP33 (3-day vs 5-day)
 - Pharmacokinetic comparison of the two infusion schedules
 - PFS per RECIST v1.1
 - DoR per RECIST v1.1
 - DCR per RECIST v1.1
- Group 3a: Head & Neck
 - DoR per RECIST v1.1
 - PFS per RECIST v1.1
 - Time to local-regional progression or distant progression per RECIST v1.1
 - Local-regional control per RECIST v1.1
 - DCR per RECIST v1.1

2.2.2.3. Exploratory Endpoints

- Assess the presence of SQP33 prodrug and active Dox in tumor tissue.
- Characterize immune response in blood and tumor tissue over time following treatment with SQ3370.

3. STUDY DESIGN

3.1. OVERVIEW

This multicenter, Phase 1/2a, first-in-human, single-arm, open-label, dose-escalation study will evaluate the safety and tolerability, PK, and preliminary efficacy of SQ3370 in patients with locally advanced or metastatic solid tumors. The Screening, Treatment, Safety Follow Up and Long Term Follow Up schedules for both the escalation and Phase 2a groups in the study can be found in the [Schedules of Assessments](#).

3.1.1. Phase 1 Dose Escalation

Patients will receive specific dose levels of SQP33 protodrug, assigned according to the dose escalation design described in section [3.2 Phase 1 Dose Escalation](#).

20 mL SQL70 Biopolymer (post-Cycle 1) Cohort:

Patients *on treatment* who attain at least a 30% reduction in injected tumor size or have a tumor that is no longer injectable may have a second lesion injected with an additional 10 mL of SQL70 biopolymer, thereby receiving a total of 20 mL of SQL70 biopolymer (see section [3.1.4.4 Phase 1: 20 mL SQL70 Biopolymer \(post-Cycle 1\) Cohort](#)).

20 mL SQL70 Biopolymer (from Cycle 1) Cohort:

To evaluate the administration of 20 mL of SQL70 biopolymer in one or two lesions starting at Cycle 1, patients will be enrolled in a separate cohort at a dose level of SQP33 protodrug that is lower than the current dose level being evaluated.

Also see the [Schedule of Assessments Appendix G](#).

3.1.2. Phase 2a Expansion Groups

Patients will be enrolled in expansion groups to further study the preliminary activity and safety of SQ3370, dosing schedules, as well as PK and immune changes in blood and tumor tissue (see section [3.3 Phase 2A Expansion](#)).

3.1.3. Screening

Screening is up to 28 days prior to starting treatment (Day -28 to Day -1). Procedures performed per standard of care during the screening period, but prior to informed consent may be used rather than repeating procedures (see section [6.2 Screening and Re-Screening](#)).

3.1.4. Treatment

3.1.4.1. Treatment Cycles

An individual cycle of treatment is defined as a 3-week (21-day) period wherein the SQL70 biopolymer is injected into a lesion or lesions on Day 1 followed by 3-5 consecutive daily infusions of SQP33 protodrug (Day 1-5 or in Phase 2a Group 2 subset will receive Day 1-3). In Phase 1 subjects assigned to receive 20 mL SQL70, no more than 2 lesions may be injected (10 mL each) during the treatment cycle with the exception of a “regional cluster of lesions”

defined as tumors that are contiguous, in apposition to each other, or are within 5 cm of each other. If there is a question whether a lesion or lesions are appropriate for injection, the Medical Monitor should be consulted.

Phase 2a Groups Specific Treatment Cycles

All patients treated at the RP2D in all groups within the Phase 2a will not be treated beyond 12 cycles or approximately 8 months.

The table below provides an overview of the SQL70 volume administered per lesion, number of potential lesions to inject, number of SQP33 timepoints per cycle and the dose to be administered each day.

Table 1: Expansion Group SQ3370 Administration Overview

Group	SQL70 Biopolymer (mL/Route)	SQP33 Protodrug RP2D IV	Daily % Dose
1: Extremity STS	20 mL intratumorally	x 5 days	20% daily x 5
2: Unresectable STS (SQP33 comparison 3 day vs 5 day)	10 mL intratumorally	x 5 days	20% daily x 5
		x 3 days	20% day 1 only 40% day 2 and 3 No Dosing on Day 4 or 5
3a: Head and Neck	10 mL intratumorally	x 5 days	20% daily x 5

Group 1: Advanced High-risk Soft Tissue Sarcoma of the Extremity

Patients will enroll at the RP2D of SQP33 given over 5 days and will receive a fixed dose of SQL70 (20 mL). On Day 1 of each cycle, the subject will receive an injection of the SQL70 biopolymer into the tumor, followed by five (5) days of SQP33 infusion at the RP2D within 3 hours \pm 30 minutes. All patients are planned to receive 2 cycles of SQ3370 and undergo a disease reevaluation per RECIST 1.1. All patients without evidence of disease progression (PD) after 2 cycles, will then undergo an additional 2 cycles of treatment and have a presurgical disease re-evaluation and proceed to definitive surgical procedure(s).

Only patients who have had objective evidence of response, or whom in the opinion of the multidisciplinary treatment team, have achieved a clinical benefit may defer surgery at this point, and the study will allow up to 4 additional pre-op cycles, at which point patients should undergo exploratory surgery and or tumor resection. It is recommended that the surgical team place markers at the tumor margins to direct SQL70 dosing post resection. Post operatively subject with good responses may receive up to 4 additional cycles but not to exceed 12 cycles within the study. Surgical markers will be used to indicate the tumor bed for injection with SQL70.

Any patient at any point who has been determined to have progressive disease has reached the end of treatment and will proceed to a definitive surgical treatment. Note: pre-operative radiation

is allowed for patients with PD pre-operatively on study at this point. It is encouraged to keep subjects on study and to evaluate surgical specimens as per planned biomarker and pathological assessments. See [Schedules of Assessments Appendix H](#).

Group 2: Unresectable Soft Tissue Sarcoma with a Comparison of the RP2D of SQP33 administered over 3 vs 5 days

Patients will enroll at the RP2D of SQP33 given over 3 or 5 days and will receive a fixed dose of SQL70 (10 mL) on Day 1 of each cycle.

To compare safety and tolerability of the RP2D in two infusion schedules of SQP33 (3-day vs 5-day) in locally advanced, unresectable, each treatment group will maintain the total dose of SQP33 per cycle and compare two different infusion schedules while receiving the same dose and timing of SQL70. All subjects will commence treatment with SQP33 within 3 hours ± 30 minutes.

Table 2: Group 2 SQP33 Protodrug RP2D (% Administered) Per Day

	Day 1	Day 2	Day 3	Day 4	Day 5
5-Day Administration	20%	20%	20%	20%	20%
3-Day Administration	20%	40%	40%	NO Treatment	NO Treatment

See Pharmacy Manual for additional details.

Any patient at any point who has been determined to have progressive disease has reached the end of treatment, any subject completing 12 cycles of treatment will also have been deemed to have reached the end of treatment. See [Schedules of Assessments Appendix I](#) and [Appendix J](#).

Group 3a: Head and Neck

Patients will enroll at the RP2D of SQP33 given over 5 days and will receive a fixed dose of SQL70 (10 mL) on Day 1 of each cycle, except for patients with a secondary lymph node lesion. These patients may receive an additional 10 mL in that lesion for a total of 20 mL of SQL70 injection. All subjects will commence treatment with SQP33 within 3 hours ± 30 minutes.

Any patient at any point who has been determined to have progressive disease has reached the End of Treatment, any subject completing 12 cycles of treatment will have been deemed to have reached the end of treatment. See [Schedule of Assessments Appendix K](#).

Note: All patients in Phase 2a expansion groups who are no longer on treatment should begin Long Term Follow Up per the [Schedule of Assessments](#).

3.1.4.2. Treatment Delays

Cycles of treatment should be administered consecutively. Consult with the Medical Monitor regarding any unexpected delays in a patient starting their next cycle. Ideally, delays between cycles should not be more than 3 weeks, i.e., at most, the patient's next cycle should start on the 4th week following the end of the previous cycle. Please consult the medical monitor to discuss patients that need to delay their next cycle for more than 3 weeks.

3.1.4.3. Treatment Duration

Patients may continue to receive treatment for up to 12 cycles (approximately 8 months). Treatment for more than 12 cycles requires approval by the Medical Monitor.

Lesions should continue to be injected until they have progressed per RECIST v1.1.

- In rare instances where the treating physician believes the patient is clearly benefiting from SQ3370 therapy despite modest radiographic progression of less than 20% that would not meet PD definition per RECIST v1.1, and following a discussion between the Medical Monitor and the treating physician, documentation in the medical record of continuation of therapy duration and criteria for continuation
- or other treatment discontinuation criteria are met (see section [3.1.5 End of Treatment](#))

In the Phase 2a study all patients may receive up to 12 cycles.

3.1.4.4. Phase 1: 20 mL SQL70 Biopolymer (post-Cycle 1) Cohort

For patients who have received treatment cycles with 10 mL of SQL70 biopolymer in Phase 1 Dose Escalation:

If the injected lesion is considered no longer injectable by the Investigator (see section [3.1.4.3 Treatment Duration](#)) then the area of the tumor bed, if possible, should be treated for two additional cycles. Additional lesion(s) may be treated with a further 10 mL of SQL70 biopolymer (for a total of 20 mL SQL70 biopolymer maximum administered per cycle) as considered appropriate by the investigator.

The administration of the additional 10 mL SQL70 biopolymer for patients already on study as described above is a separate group of patients from the cohort that will receive 20 mL SQL70 biopolymer beginning at Cycle 1 (see section [3.2.3 Phase 1: 20 mL SQL70 Biopolymer \(from Cycle 1\) Cohort](#)).

3.1.5. End of Treatment

The patient, Investigators, and/or the Sponsor may decide to end a patient's treatment at any time. The Safety Follow-Up Visit should be performed approximately 30 days after the last dose of study drug (see section [3.1.6 Safety Follow-Up Visit](#)).

Reasons that the patient, Investigators, and/or the Sponsor may decide to end (discontinue) a patient's treatment include:

- Radiographic progression of disease per RECIST v1.1
- Unacceptable AE(s)
- Initiation of radiotherapy or non-protocol tumor directed treatment
- Any medical condition or treatment that the Investigator or Sponsor determines may jeopardize the patient's safety if he or she continues in the study
- Patient noncompliance with study procedures
- Patient inability to attend visits (e.g., patient moves, change in caregiver)

- Patient withdrawal of consent to treatment
- Patient withdrawal of consent to treatment and follow-up
- Investigator decision
- Sponsor decision
- Lost to follow-up
- Death

3.1.6. Safety Follow-Up Visit

The Safety Follow-Up visit is either:

- within 28 to 34 days after the patient's last dose of SQL70 biopolymer or SQP33 protodrug, whichever was last administered
- or prior to the start of a new anticancer treatment

3.1.7. Long Term Follow-Up

Long Term Follow-Up visits commence after the patient's last cycle of treatment, every 12 weeks (± 7 days) for up to two years. See [Schedule of Assessments](#) for the list of procedures performed at the visits.

All patients that discontinue treatment will be followed for information on progression, if treatment discontinuation was not RECIST 1.1 progression, and overall survival. Additional information will be obtained for next line of treatment and survival status.

[figure not shown]
This long term follow-up information will be gathered during routine clinic visits, other study site contact with the subjects, or via telephone or e-mail with the subjects/caregivers or referring physician offices.

If the study is closed, Long Term Follow-Up visits will stop.

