Only patients who have had objective evidence of response or whom in the opinion of the multidisciplinary treatment team determined to have achieved a clinical benefit may defer surgery at this point, the study will allow up to 4 additional cycles pre-operatively, at which point all patients should undergo exploratory surgery and or extremity tumor resection.

If a patient had a response, they may receive up to 4 additional cycles post operatively but not to exceed 12 cycles within the study. Surgical markers will be used to indicate the tumor bed for injection with SQL3370 or if suitable for the metastatic patients, a metastatic lesion may be injected.

Any patient at any point who has been determined to have progressive disease has reached the end of treatment and will proceed to a definitive surgical treatment, note pre-operative radiation is allowed on study for patients with progressive disease preoperatively. It is encouraged to keep subjects on study and to evaluate surgical specimens as per planned biomarker and pathological assessments.

Patients who undergo surgical resection and have had good response as defined by necrosis on histopathological resection may continue for additional treatment post-operatively. If post op radiation is administered the subjects come off treatment (see [3.1.5 End of Treatment](#) for details) and will remain on study in Long Term Follow-up.

Safety Monitoring

The Study will use a safety-run-in to evaluate the PK and tolerability when at least 6 subjects have been enrolled and completed at least the planned Cycle 1. All available safety tolerability data will be presented and discussed at the SRC.

If after the evaluation by the SRC the study proceeds after evaluation of the initial subjects a second evaluation as defined in the statistical section. An evaluation of the totality of the data available to complete the planned 4 cycles and to review efficacy and histopathological response data and will provide the sponsor a recommendation as to proceed with expansion or to halt enrollment of the group.

Group 2: Comparison of the RP2D of SQP33 Administered Over 3 vs 5 Days

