6.18. CT/MRI TUMOR IMAGING & MEASUREMENTS

All measurements should be taken and recorded in metric notation using a ruler, calipers, or a digital measurement tool.

The same method of assessment and the same imaging technique regarding modality, ideally the same scanner, and the use of contrast should be used in a participant throughout the study

to optimize the reproducibility of the assessment of existing and new tumor burden and improve the accuracy of the assessment of response or progression based on imaging.

Assessment should be performed:

- During screening
- Every 6 weeks (-7-day window) from Cycle 1 Day 1 until end of treatment
- At the Safety Follow-Up Visit, if not performed in the previous 6 weeks
- If a patient comes off treatment due to non-RECIST progression, a scan should be obtained during Long Term Follow Up, until radiographic progression is noted.
- Additional scans may be conducted at other time points if deemed clinically appropriate

Scans will be read at the study site. Scans must include chest, abdomen, and pelvis, as well as any other areas of disease, whether or not measurable, present at screening and/or follow-up, including extremities.

Computed Tomography (CT) / Magnetic Resonance Imaging (MRI): Scans are required to document disease status (including chest, abdomen, pelvis, and other regions as clinically indicated). A brain scan is required to exclude brain metastasis if clinically indicated.

Clinical Examination: Imaging-based evaluation is preferred to evaluation by clinical examination unless the lesion(s) being followed cannot be imaged but are assessable by clinical examination. Tumors may also be assessed utilizing visual or palpable lesions on physical examination, including full assessment of all known metastases.

Copies of redacted radiology reports and interventional radiology procedure notes may be obtained for quality control.

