K - ECHO or MUGA not required at the Safety Follow-Up visit if performed in the previous 14 days.

L - CT / MRI & RECIST not required at the Safety Follow-Up visit if performed in the previous 6 weeks.

M - For up to 2 years after treatment end; collected during routine clinic visits, telephone or e-mail with the subjects/caregivers or referring physician offices.

N - Until disease progression per RECIST; May be performed up to 14 days before the visit.

O - PBMC and ctDNA tubes are included in the same kit but are separate tubes. Collection is done on D1 of C1-3 only.

Reminder: Investigator can perform unscheduled labs, ECGs and physical exams as needed / clinically indicated.

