11.11 Distant Recurrence-Free Survival (Group 1)

Distant-recurrence free survival is defined as time between the date of enrollment and the date of distant recurrence/relapse or death from any cause, whichever occurs first.

At this time, there is not enough information regarding this endpoint. The data collection and planned analysis of this endpoint will be discussed in the next version of this SAP after the safety run-in and/or Simon Stage 1 analysis. However, Kaplan-Meier methods will be utilized for data analysis of this endpoint.

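### Scheduled tumor follow-up ends at first RECIST progression, so local and distant recurrence-free survival in Group 1 are incompletely ascertained

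*Protocol*

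**What the plan says.** Three places in the protocol decide when tumor follow-up stops.

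- Section 3.1.7 (Long Term Follow-Up): "All patients that discontinue treatment will be followed for information on progression, if treatment discontinuation was not RECIST 1.1 progression, and overall survival". The visits run "every 12 weeks (± 7 days) for up to two years", and "Additional information will be obtained for next line of treatment and survival status".
- Section 6.18, for patients who come off treatment without RECIST progression: "a scan should be obtained during Long Term Follow Up, until radiographic progression is noted".
- Appendix H note N, on long-term scans in Group 1: "Until disease progression per RECIST; May be performed up to 14 days before the visit". Apart from those scans, the long-term column of Appendix H lists only vital status.

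For Group 1, section 3.1.4.1 says that a patient with progressive disease at any point "has reached the end of treatment and will proceed to a definitive surgical treatment". Section 3.5.1 repeats this.

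The endpoints are defined in protocol section 8.4.2.2 and the Phase 2a SAP. SAP 11.11 reads: "Distant-recurrence free survival is defined as time between the date of enrollment and the date of distant recurrence/relapse or death", whatever the cause of death. SAP 11.10 is the parallel definition for local recurrence, which carries a 2-year time frame. Neither definition ends at an event of the other type. Disease-free survival (SAP 11.9) ends at the first recurrence of any kind or death. For all three, the SAP leaves data collection and analysis to its next version and commits only to Kaplan-Meier estimation.

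**The concern.** A schedule that stops at first progression suits progression-free survival, where nothing later matters. Local and distant recurrence-free survival are different: each must be watched for after an event of the other type. Under Tables 6 and 7 of section 6.18.2 a new lesion is progression, so a first recurrence at either site closes the scan schedule for the other.

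The gap is widest for patients who progress before surgery. They are operated on while on study, and the two endpoints are meant to describe what follows, yet nothing scheduled looks for it. If sites are never asked for the date and site of later events, a later SAP version cannot recover them. The two estimates would then rest on incomplete data in patients who may well be at higher risk.

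**Working it through.** **1. The plan's own figures.** The only design figures for Group 1 concern response rate (section 8.3: stop at 3 or fewer of 15, reject at 13 or fewer of 46, 20% against 35%). An exact binomial calculation gives alpha 0.0498, power 70.5%, stopping probability 0.648 and expected size 15 + (1 − 0.6482) × 31 = 25.91. All agree with the plan. They say nothing about recurrence, for which no figure is stated.

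**2. Schedule against endpoint.**

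| Group 1 patient | Scheduled tumor assessment afterwards | Endpoint still open |
|---|---|---|
| Progresses before surgery | None | Local and/or distant, depending on the site of progression and how it is counted |
| First recurrence local | None | Distant |
| First recurrence distant | None | Local |

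Death is still captured and is an event in both endpoints. Disease-free survival has already ended in the last two rows.

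**3. How many patients.** The documents give no rate of progression before surgery. Assuming 20% to 40%: 0.2 × 46 = 9 to 0.4 × 46 = 18 patients if Group 1 fills, or 3 to 6 if it stops at 15.

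**4. Illustration A: distant event after a local one.** All inputs are assumptions: median 24 months to local and to distant event, 48 months to death, and a shared gamma frailty with variance v. At 24 months the cumulative hazards are 0.693 (local), 0.693 (distant) and 0.347 (death). Distant plus death is 1.040; all three total 1.733.

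- Complete follow-up: (1 + 1.040v)^(−1/v)
- Censored at the local event: (1 + 1.733v)^(−0.6/v), where 0.6 = 1.040/1.733
- Carried forward to death: ½(1 + 0.347v)^(−1/v) + ½(1 + 1.733v)^(−1/v)

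| v | Complete | Censored | Carried forward |
|---|---|---|---|
| 0.5 | 43.3% | 47.3% (+4.0) | 50.7% (+7.4) |
| 1 | 49.0% | 54.7% (+5.7) | 55.4% (+6.4) |
| 0 (limit) | 35.4% | 35.4% (0) | 44.2% (+8.8) |

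The bias under censoring comes entirely from the assumed frailty. Carrying forward overstates even without frailty.

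**5. Illustration B: progression before surgery.** The base distant hazard takes the 49.2% metastasis figure for amputation patients in protocol section 1.1.1 and assumes it is reached by 36 months: −ln(0.508)/36 = 0.0188 per month. Further assumptions: local progression at 1.4 or 2.8 months in 10% to 40% of patients; distant hazard afterwards multiplied by HR; mean 18 months from distant event to death; no other deaths. Simulated 24-month distant recurrence-free survival (400,000 patients):

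| Progressing | HR | Complete | Censored at progression | Only death counted | Progression counted as event |
|---|---|---|---|---|---|
| 20% | 1 | 63.7% | 63.7% | 67.3% | 50.9% |
| 20% | 2 | 59.4% | 63.8% | 65.2% | 51.0% |
| 40% | 3 | 49.4% | 63.7% | 63.3% | 38.2% |

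Over 10% to 40% progressing and HR 2 to 3, censoring or counting only deaths overstates by about 2 to 14 points. Over HR 1 to 3, counting progression as an event understates by about 3 to 26 points.

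**The case against.** A reader might infer that these patients get no recurrence follow-up, that later events are never seen, and that recurrence-free survival is overstated in general. The documents do not support that.

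- **Follow-up does not cease.** The 12-weekly contacts go on, section 3.1.7 collects next therapy and survival, section 6.18 allows extra scans if clinically appropriate, and deaths count as events. Sections 3.1.4.1 and 3.5.1 encourage keeping progressors on study, though the purpose they name is surgical specimens. Some later recurrences may come to light. What is missing is a scheduled assessment and a place to record site and date. Next therapy supplies neither, and Appendix H note M does not repeat the instruction to capture it that Appendices I to K carry.
- **Direction is not settled.** The SAP has no censoring rule for these endpoints and does not say how progression before surgery is counted. Treating a local progression as a distant event would sit badly with the definition of distant recurrence-free survival, but no text excludes it.
- **Disease-free survival** is not affected by a missed second event.
- **Stakes are limited.** These are secondary, descriptive, single-arm endpoints; the primary endpoint is safety and the Simon rules use response.

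All of this stands and narrows the point. Deferring the analysis to a later SAP does not answer it, because the stopping rule is in the protocol and decides what data will exist.

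**Conclusion.** The concern holds in a limited form. The protocol's rule for ending tumor follow-up conflicts with two Group 1 secondary endpoints as defined, so both local and distant recurrence-free survival are incompletely ascertained, most plainly after progression before surgery.

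The likely effect, if such patients are censored or carried forward to death and local and distant risk are positively correlated, is an overstatement of 24-month distant recurrence-free survival. The size of about 4 to 7 points in illustration A rests on assumed event rates and frailty and does not model surgery; illustration B shows how widely the answer moves with other assumptions. Neither is an estimate for this trial.

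Group 3a has the same schedule gap (Appendix K note N). No bias is claimed there, because local-regional control has no definition in SAP 11.14, and time to local-regional or distant progression ends at the first event anyway.

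**What to change.** - **Protocol 3.1.7 and Appendix H:** for Group 1, at the existing 12-weekly contacts for up to 2 years, record the date and site (local, regional, distant) of any recurrence or progression found on routine imaging, regardless of earlier RECIST progression.
- **Phase 2a SAP 11.10 and 11.11:** state that an event of one type does not end follow-up for the other, how progression before surgery is counted in each endpoint, and when patients are censored.
- **Group 3a:** the same item can be collected, but local-regional control must first be defined in SAP 11.14.

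Cost: a protocol amendment, one eCRF item and SAP wording. No extra scans are mandated, so assessment after progression stays unscheduled, event dates will depend on local imaging practice, and the report should say so. The change is best made before more Group 1 patients pass progression or surgery.
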